21.6 Reporting of SAEs from sites to the CTU study team

Only serious adverse events considered by the site investigator to be related (possibly, probably, or definitely) to the study intervention/any of the research procedures will be reported immediately to the central CTU study team. Such events will be reported immediately to the study team as follows:

SAEs will be reported by the site research team using the SAE form within REDCap within 24 hours of becoming aware of the event. The CTU is automatically notified of the SAE report via REDCap. A paper SAE form should be used as a back-up if the SAE form is not available electronically. This should be emailed to central study e-mail ([contact]) within 24 hours of becoming aware of the event. The central CTU study team will acknowledge receipt of any SAEs reported via email within one working day and provide the site with a unique SAE Log number.

Refer to Section 21.4 for events that do not require reporting.

21.7 Assessment of SAEs by the Principal Investigator (or delegate)

The Principal Investigator (or delegated individual) is responsible for assessing all reported serious adverse events for seriousness, causality and expectedness.

21.7.1 Relatedness/causality

The assessment of "relatedness" to the study intervention is the responsibility of the PI at site or an agreed designee according to the following definitions:

ACL STARR_Protocol_V2.0_03Feb2025.docx

Relationship to intervention	Attribution (Causality)	Description
Unrelated	Unrelated	The AE is clearly NOT related to the intervention
	Unlikely	The AE is doubtfully related to the intervention
Related	Possible	The AE may be related to the intervention
	Probable	The AE is likely related to the intervention
	Definite	The AE is clearly related to the intervention

21.8 Review of SAEs by the Sponsor/CTU Nominated Person

An appropriately qualified person will review the SAE and raise any queries with the reporting site. If the site has not provided an assessment of causality and has not responded to the query, it will be assumed that the event reported is related to the study procedures/intervention. The site will be encouraged to respond and if a response is not provided the CI will be consulted by the CTU and the CTU will complete the Sponsor part of the SAE report.

21.9 Reporting of SAEs to the Research Ethics Committee (REC)

All intervention/study procedure related SAEs will be recorded and reported to the REC as part of the annual reports. All SAEs that are assessed as related and unexpected will be submitted to the REC within 15 days of the CTU/Sponsor becoming aware of the event.

21.10 Unblinding of SAEs for reporting to the REC

Any serious unexpected SAEs that require reporting to the REC will be unblinded for reporting purposes. Unblinding will be performed, documented and communicated in accordance with OCTRU Standard Operating Procedures.

21.11 Follow-up of Serious Adverse Events

If the SAE is an unexpected, related event then follow up information must be provided as requested by the central CTU study team. A follow-up report must be completed when the SAE resolves, is unlikely to change, or when additional information becomes available.

22 PREGNANCY

If a participant does become pregnant during their participation in the study, it does not need to be reported due to the nature of the intervention as concluded in the risk assessment of the study.

23 STATISTICAL CONSIDERATIONS

23.1 Statistical Analysis Plan (SAP)

The statistical aspects of the study are summarised here with details fully described in a statistical analysis plan (SAP) that will be drafted early in the study and finalised prior to the final analysis data lock, or any planned interim comparative analyses. The SAP will be written by the Study Statistician in accordance with the current OCTRU SOPs. The TSC and DSMC will review and, if necessary, provide input into the SAP.

23.2 Sample Size/Power Calculations

The sample size calculation was premised upon a 1:1 randomised parallel group trial design with an analysis of the primary outcome (KOOS-4) using mixed-effects linear model adjusted for randomisation variables and baseline KOOS-4. Standard nominal 2-sided 5% significance level was adopted, and the power for detecting a between group difference of 8 and 9 points in the KOOS-4, was assessed for a missing data allowance of 15%.

We considered a variety of scenarios varying the adjustment for baseline correlation and desired statistical power. (See Table 4 below for a selection)

Table 4 – Sample size scenarios; all based upon 2-sided 5% significance level, 1:1 allocation continuous outcome, pooled SD of 20, and non-central-t distribution calculation [Stata power two means command]

No.	Target difference	Statistical Power	Missing data allowance	Adjusted for baseline	Sample size required (overall)
1	8	80	15%	No	236
2	8	90	15%	No	314
3	9	80	15%	No	186
4	9	90	15%	No	248
5	8	80	15%	Yes	204
6	8	90	15%	Yes	272
7	9	80	15%	Yes	162
8	9	90	15%	Yes	214

An overall sample size of 236 and 186 is required for 80% power for a difference of 8 points and 9 points respectively given a pooled standard deviation (SD) of 20 points. Equivalent 90% power, required number of observations are 314 and 248 respectively.

However, the expected sample size required is lower given the planned adjustment for baseline KOOS-

4 score as the effective variability is reduced. Implementing this using the formula provided by Borm⁽³⁹⁾ using a correlation between baseline and follow-up score of 0.37 leads to requiring only 204 and 272 for 80% and 90% power for a target difference of 8 points or equivalently 162 and 214 (all other assumptions and inputs as before) for 9 points difference. Therefore, we have opted for a sample size of 214 (no. 8, table 2) randomised participants which allows for 15% missing data for a target difference of 9 points (at 90% power). This sample size also ensures more than 80% power for a target difference of 8 points (no. 5, Table 2).

We anticipate that 25% of those who consent to be assessed as unsuitable for repair intra-operatively, we expect approximately 286 will need to be consented. The intraoperative assessment at arthroscopy has been shown to be crucial to determine the repairability of the ligament and reduce failure rate $^{(40)}$.

Justification of sample size inputs

Target difference: The selected target difference was informed by a review of the relevant literature conducted for the ACL SNNAP study which was updated for this submission. The Minimal Important Change (MIC) for the KOOS score is 8-10 points. Estimates of the Minimal Detectable Changes (MDC) for the two KOOS subscales most relevant for ACL deficiency (ACLD) vary between 5 and 12 points (Symptoms= 5-8.5 and Sport/Rec=6-12)⁽⁴¹⁾. A more recent review of the literature specifically for studies assessing meaningful values in the KOOS and other candidate patient reported outcome score for ACL tears or traumatic meniscus injuries) did not indicate a different value for KOOS or that another outcome had better research on meaningful differences⁽⁴²⁾. Study findings agree with a search in PubMed review conducted for the study funding proposal (13 June 2023) of studies assessing clinical important differences in the KOOS score. The recently published ACL-SNNAP demonstrated that a mean difference of 8 points is possible between interventions and that this magnitude of difference related to tangible differences in other knee specific patient reported outcome, generic measure of patient satisfaction (would you have the treatment again if you could go back, and assessment of knee after versus before). We note that while figures such as 0.2 or 0.3 SD are regularly quoted patientreported quality of life measures do differ in their underlying properties, and estimates for important differences in the literature have varied⁽⁴³⁾. It has been suggested that 0.5 SD is a more appropriate standard deviation (SD) for the minimally important difference for quality of life⁽⁴⁴⁾, which would equate to a target difference of around 10 points here if implemented (i.e. "Cohen's effect size" distribution approach). We have used target difference values of 8 and 9 points when considering various sample size scenarios which the current evidence on important differences and responsiveness suggest are reasonable estimates of a minimal clinically important difference (MCID) for the KOOS-4 outcome.

Standard deviation: The (pooled) SD value of 20 was based upon the observed value in the ACL SNNAP study at 18 months (19.9 pooled SD). Given the target population in ACL STARR is more homogenous the SD may well be slightly lower.

Correlation between KOOS-4 24 month and baseline scores: This was based upon KOOS-4 data from the ACL SNNAP study. The 6-, 12- and 18-month KOOS-4 scores had similar Pearson correlation values to baseline (0.42, 0.41 and 0.37 respectively). We used the lowest of these values 0.37 in the corresponding sample size calculations.

Missing data: The selected sample size of 214 (randomised) incorporates an allowance of 15% missing data by 24 months. Based upon previous studies this seems a reasonable level. ACL SNNAP had 22% missing data at 18 months though the follow-up pathway for reconstruction/repair is different from rehabilitation. Additionally, we believe we have improved our retention process from this study and believe 15% is a realistic level.

Intraoperative suitability: Finally, the number needed to be randomised was inflated to allow for unsuitability for repair being identified intraoperatively. The required randomised number (214) was inflated by 25% to 286. This is due to the loss of integrity of the synovial sheath that surrounds the ACL. The figure of 25% unsuitability was based upon previous research. Atteschrang et al⁽⁴⁰⁾ show the importance of the synovial sheath in determining the repairability of the ligament, and subsequent outcomes.

23.3 Description of Statistical Methods

The statistical analyses will be performed once the 24 months follow up has been reached by the last patient and sufficient time has been allowed for data collection and cleaning.

Results will be reported in line with the Consolidated Standards of Reporting Trials (CONSORT) statement and any appropriate extensions and will be described fully in a separate Statistical Analysis Plan. The SAP will be finalised prior to un-blinding of the data to clinical investigators and after consultation with investigators and other relevant stakeholders.

Nominal 2-sided 5% significance level will be used throughout. Subgroup analyses will be indicated as exploratory and non-planned analyses as "post-hoc".

Intention-to-treat (ITT) will be the main analysis strategy and will be adopted for the primary and all secondary outcomes. In other words, the analysis will principally be focussed on a treatment policy estimand. As patients are randomised in theatre, following surgeon confirmation of suitability, non-compliance is expected to be minimised and intercurrent events more limited than in a typical NHS based surgical study (e.g. no post-randomisation timing of surgery mediation). However, some repairs may still be abandoned, perioperatively and post randomisation. Rates of compliance will be monitored throughout the study, including the pilot phase. Two secondary analysis populations will therefore be conducted on the primary outcome: a per-protocol analysis, that mirrors ITT but excludes patients with major protocol deviations, and an as-treated analysis, where patients are classified according to the treatment received. These secondary analyses will assess robustness of ITT analysis and any deviation from routine clinical practice. The handling of such events will be agreed in advance of conducting the analysis and detailed in the SAP.

The main analysis will be conducted using a complete case approach with no planned imputation for missing data. An independent Data and Safety Monitoring Committee (DSMC) will meet early in the study to agree its terms of references. They will review confidential interim analyses of the stop-go criteria and monitor within patient correlation of KOOS-4 scores between baseline and 24 months and compliance to randomised treatment.

It is anticipated that all statistical analysis will be undertaken using Stata (StataCorp LP, www.stata.com) or other validated statistical software.

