13.1 ACL repair (intervention)

Participants randomised to ACL repair will have surgery to repair the ACL, with the ligament being stitched back onto the bone. This study specifies that surgery (for both repair and reconstruction), is undertaken no more than 50 days post injury (please see Section 28.7 for details of protocol deviations). This is a pragmatic approach, aligning with existing literature, which indicates that time to surgery is an important factor in primary repair outcomes (6), while also being mindful of the pressure on NHS waiting lists.

There are several techniques to re-attach the ACL to its footprint. Each technique may require different instruments and devices, but all have the same principle of re-attachment. The study is devoid of commercial interest with no single preferred technique or device. The techniques that can be used are well described within the literature, and included in the Surgical Manual. All surgeons will have the necessary skill set and experience to undertake the repair (peer review). We will not be allowing new

or innovative techniques to be undertaken within the study. Currently, only the two most common repair techniques are approved for use in ACL STARR. This decision was made following consensus consultation and to ensure consistency and external validity. The two options are: 1) suture anchors or 2) transosseous suture repair. The list (in the Surgical Manual) will be kept under review by the Trial Management Group (TMG) and discussed with the Trial Steering Committee (TSC) throughout to ensure the current list is representative of current practice.

Feedback from the surgeon co-applicants highlighted that repair can be a technically challenging procedure and, on occasion, can be abandoned midway through operation. We are aware of this potential crossover and have attempted mitigation in both patient selection criteria and analysis. Oversight of the potential for crossover will be maintained especially in the initial pilot phase.

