15.3 Randomisation methodology

Participants will be randomly allocated to one of two treatment options (1:1) via automated, secure (encrypted), web-based randomisation provided by the Oxford Clinical Trials Research Unit (OCTRU) using a REDCap platform.

Random allocation will be implemented using a minimisation algorithm with stratification factors: preinjury Tegner score (2 groups (0-6, 7-10)), planned lateral extra-articular procedure (yes, no) and site. The minimisation algorithm will be seeded with several allocations and a non-deterministic probabilistic element will be introduced to prevent predictability of the treatment allocation.

Patients not randomised in theatre will be managed along the normal standard of care pathway.

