28.7 Protocol Compliance and Deviations

Protocol compliance is fundamental to GCP. Prospective, planned deviations or waivers to the protocol are not allowed. Changes to the approved protocol need prior approval unless for urgent safety reasons.

A study related deviation is a departure from the ethically approved study protocol or other study document or process or from Good Clinical Practice (GCP) or any applicable regulatory requirements. Deviations from the protocol will be captured in REDCap using either using a protocol deviation form or via suitably designed fields within the CRF which will be extracted from REDCap and reviewed

regularly by the Trial Management Group (TMG). Deviations will be handled and reviewed in a timely manner in accordance with a study-specific Data Management and Monitoring Plan.

For ACL STARR, the acceptable time from injury to surgery has been defined as 50 days. If this is exceeded, it will be reported as a protocol deviation. This is a pragmatic approach, aligning with existing literature, which indicates that time to surgery is an important factor in primary repair outcomes⁽⁶⁾, while also being mindful of the pressure on NHS waiting lists.

If the participant is randomised to repair surgery in theatre, and there is an unplanned intraoperative conversion to reconstruction surgery, e.g. if the ligament was thought to be repairable, but further surgical evaluation indicates the need for a reconstruction, the participant will be permitted to crossover to the reconstruction arm and will remain on the study.

The investigator must promptly report any important deviation from Good Clinical Practice or protocol to the central CTU study team. Examples of important deviations are those that might impact patient safety, primary/ secondary endpoint data integrity, or be a possible serious breach of GCP.

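### Per-protocol and as-treated analyses cannot test the robustness of ITT when the only crossover described is repair converted to reconstruction after randomisation

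*Protocol*

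**What the plan says.** Section 23.3 makes ITT, with a treatment policy estimand, the main strategy. It accepts that some repairs may be abandoned after randomisation and for that reason adds two analyses of the primary outcome. One is per-protocol, excluding major protocol deviations; the other is "an as-treated analysis, where patients are classified according to the treatment received". Their purpose is stated: "These secondary analyses will assess robustness of ITT analysis and any deviation from routine clinical practice". How the events are handled is left to the SAP.

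The crossover itself is described in two other places. Section 13.1 reports surgeons' advice that "repair can be a technically challenging procedure and, on occasion, can be abandoned midway through operation". Section 28.7 lets a participant allocated to repair cross over to reconstruction and remain in the study, giving as an example the case "if the ligament was thought to be repairable, but further surgical evaluation indicates the need for a reconstruction". Crossover from reconstruction to repair is not described anywhere. The sensitivity analyses in section 23.3.1 deal with age and missing data, not with abandoned repairs.

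**The concern.** A robustness check should rest on assumptions different from those of the main analysis and should not bring in a predictable bias of its own. Here both checks regroup or remove participants because of one event that happens after randomisation, can depend on what the surgeon finds, and can be seen in one arm only.

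- **As-treated** moves every converted knee into the reconstruction group. This follows from its definition and needs no further ruling.
- **Per-protocol** drops converted knees from the repair arm if conversion is a major deviation, while the same kind of knee stays, unseen, in the reconstruction arm because no repair is attempted there.

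If those knees have a worse outlook, both estimates drift towards repair through the same mechanism. Agreement with ITT, or between the two, would then say little. A marginal ITT result could seem confirmed by analyses that cannot confirm it, and a null ITT result could sit beside a favourable secondary estimate.

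**Working it through.** **1. The plan's own figure.** Section 23.2 states: "Standard nominal 2-sided 5% significance level was adopted". Its other inputs are 1:1 allocation, "given a pooled standard deviation (SD) of 20 points", and "using a correlation between baseline and follow-up score of 0.37". For 9 points at 90% power the noncentral-t calculation gives 105 per arm, or 210. Baseline adjustment gives 210 × (1 − 0.37²) = 181.3 complete cases. Then 181.3/2/0.85 = 106.6, rounded up to 107 per arm, or 214. This matches Table 4, row 8; the other seven rows also reproduce. About 107 × 0.85 = 91 per arm would be analysed, with adjusted SD 20 × √(1 − 0.37²) = 18.6.

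**2. Assumptions.** The protocol gives no conversion rate and no outcome difference for converted knees. Let x be the share of the repair arm converted. Let D be the KOOS-4 deficit of such knees when reconstructed, present equally but unseen in the reconstruction arm. Take no true effect and no harm from the attempt. Other knees have mean m.

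**3. Formulas.** Each randomised arm has mean m − xD, so ITT is unbiased.

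- Per-protocol, conversions excluded: m − (m − xD) = xD.
- As-treated: the reconstruction group has mean [(m − xD) + x(m − D)]/(1 + x) = m − 2xD/(1 + x), so the bias is 2xD/(1 + x).

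A simulation of 4 million patients at x=10%, D=10 agrees with both formulas.

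**4. Bias in KOOS-4 points (positive favours repair).**

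| x | D | Per-protocol | As-treated |
|---|---|---|---|
| any | 0 | 0 | 0 |
| 2% | 5 | 0.10 | 0.20 |
| 5% | 5 | 0.25 | 0.48 |
| 10% | 5 | 0.50 | 0.91 |
| 10% | 10 | 1.00 | 1.82 |
| 20% | 10 | 2.00 | 3.33 |
| 10% | −5 | −0.50 | −0.91 |

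Against the 9-point target, x=10%, D=10 is 11% and 20%; x=20%, D=10 is 22% and 37%.

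**5. Effect on error rates.** Take 91 per arm, SD 18.6, x=10%, D=10. The standard error is 18.6 × √(1/81.9 + 1/91) = 2.83 for per-protocol and 18.6 × √(1/81.9 + 1/100.1) = 2.77 for as-treated. The chance of a false finding in favour of repair, nominally 2.5%, becomes 5.4% and 9.6%. At x=2%, D=5 it is 2.7% and 2.9%.

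**6. A randomisation-based alternative.** With one-way conversion the complier-average effect is ITT/(1 − x).

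| Scenario (x = 10%) | ITT | Per-protocol | As-treated | Complier-average |
|---|---|---|---|---|
| No effect, D=10 | 0.0 | 1.0 | 1.8 | 0.0 |
| Effect 9 in completed repairs, D=10 | 8.1 | 10.0 | 10.8 | 9.0 |
| No effect, D=0, abandoned attempt costs 10 points | −1.0 | 0.0 | 0.9 | −1.1 |

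In the last row as-treated charges the harm of the failed attempt to reconstruction, and the complier-average estimate is also wrong, because its key assumption fails.

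**The case against.** The strongest reply concerns direction. A reader might infer that both analyses favour repair by construction. The documents do not support that. Section 8 says the torn ligament is removed in reconstruction, so its quality may not affect the result once a graft is in place. Section 23.2 links the synovial sheath to outcomes, but in the setting of repairability. Every randomised knee has already passed inspection at arthroscopy. An unrepairable ligament is only an example in section 28.7, and technical difficulty, the reason in section 13.1, need not mark a worse knee. With D=0 and no harm from the attempt the bias vanishes; with D negative it reverses. All of this stands, so the direction is conditional.

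Three more points stand in part.

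- Per-protocol is affected only if conversion is a major deviation, which the protocol leaves open. But section 23.3 introduces the analysis because repairs may be abandoned. If conversions are kept, it does not address the event that prompted it. The as-treated definition has no such gap.
- Non-compliance is expected to be low, and at x=2% the bias is negligible.
- A reader might infer that the trial's conclusion is at risk. It is not: ITT is the principal analysis in sections 23.3 and 23.4, and nothing lets a secondary analysis override it.

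Finally, the complier-average estimate and its standard error both scale by about 1/(1 − x), so its test is nearly the ITT test. It adds an effect size for completed repairs, not a fresh challenge to ITT. That is a reason to add it as a supplement and not to oversell it.

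**Conclusion.** The point holds in conditional form. What section 23.3 fixes now is the choice of two analyses and the claim that they assess the robustness of ITT; that claim is not sound. As-treated loses the randomised comparison whatever the SAP says, and per-protocol does so if conversions are excluded. The likely direction is towards repair if converted knees do worse even when reconstructed. For as-treated, harm from the abandoned attempt acts the same way. As-treated bias is 2/(1 + x) times that of per-protocol, so nearly double. The size runs from a few tenths of a point at low x to 1.0 and 1.8 points at x=10%, D=10, with x and D assumed throughout. Uncertainty about the sign does not rescue the robustness claim: a check whose bias cannot be signed or sized from the trial's data is still not a test of ITT. The primary analysis is unaffected.

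**What to change.** In section 23.3, and in the SAP to match:

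1. Keep ITT as the primary analysis.
2. Add a complier-average causal effect analysis of 24-month KOOS-4, with randomised arm as the instrument for repair received, the primary model's covariates, and a stated allowance for site. Ordinary two-stage least squares does not reproduce the random site effect, so the SAP should say how site enters.
3. Label the per-protocol and as-treated analyses descriptive, and remove the statement that they assess the robustness of ITT.
4. Report the complier-average result together with its assumption that allocation acts only through the operation received, and say that this fails if an abandoned repair attempt itself affects outcome.

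The cost is a wording change and one extra model on data already collected. The standard error rises by about 1/(1 − x), or 11% at x=10% (1/0.9 = 1.11), and the test adds little beyond ITT. The change is best made before conversion rates by arm and outcomes are known.
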